**Updated power estimations with additional objectives (Protocol Amendment 5):**

Based on live blinded data observed from Cohort 1, the estimated attrition rate of Cohort 1 was adjusted from 15% to about 13.5% at both D28 and D42 for pediatric subjects, and adjusted to about 21.0% at D28 and 19.8% at D42 for adult subjects, respectively. Assuming the actual attrition rate of adult subjects in Cohort 2 is similar to Cohort 1, the adjusted estimations for evaluable number of subjects in the PPAS in each age group are as below:

- Pediatric subjects (Cohort 1 only): at both D28 and D42, there will be about 261 and 88 evaluable subjects in VRVg-2 group and each of the comparator vaccine groups, respectively.
- Adult subjects: at D28, there will be about 570 and 190 evaluable subjects in VRVg-2 group and each of the comparator vaccine groups, respectively (pooled Cohort 1 and Cohort 2); at D42, there will be about 243 and 81 evaluable subjects in VRVg-2 group and each of the comparator vaccine groups, respectively (Cohort 1 only).

Moreover, 2 new secondary immunogenicity objectives were added as below, both with a NI margin of -10%:

- Secondary immunogenicity objective 3: To demonstrate the NI of a 2-dose VRVg-2 PrEP at D28 versus 3-dose Imovax Rabies PrEP at D42 in each age group
- Secondary immunogenicity objective 5: To demonstrate the NI of a 2-dose Imovax Rabies PrEP at D28 versus 3-dose Imovax Rabies PrEP at D42 in the overall subjects (pooled pediatric and adult subjects) in Cohort 1

Finally, the primary objectives and all 5 key secondary immunogenicity objectives will be evaluated sequentially. Each of the key immunogenicity objective will be tested only if the previous objective is achieved.

Based on the updated study objectives and the adjusted number of evaluable subjects, the power to demonstrate each of the key immunogenicity objectives is presented as below:

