12.5 Determination of Sample Size and Power Calculation

12.5.1 Primary Series

Original Plan for Cohort 1:

An alpha level of 2.5% (one-sided hypothesis), has been chosen to calculate the sample size.

Originally, assuming a proportion of subjects with an RVNA titer ≥ 0.5 IU/mL of 99% for both VRVg-2 and control vaccines in each age group at D42, a clinical acceptable difference of -5% for the difference of proportions at D42 between VRVg-2 and the control vaccines, and a power of

at least 95% for each of the NI testing in the primary objective, with and an unbalanced randomization ratio of 3:1:1 (VRVg-2: Verorab vaccine: Imovax Rabies vaccine), 258 evaluable subjects in the VRVg-2 group, and 86 evaluable subjects in each of the Verorab and Imovax Rabies vaccine groups who are planned to receive 3 vaccinations (at D0, D7 and D28) in primary series in each age group, will be necessary to provide a global power of 81.8% for the primary NI objective, using the Farrington and Manning (FM) method.

If the primary objective is met at D42, a total of 516 subjects evaluable in the VRVg-2 group will ensure 85.0% of power for the 1st secondary immunogenicity objective of superiority at D42. If the 1st secondary immunogenicity objective is met, overall power for the 2nd secondary immunogenicity NI objective of 2-dose VRVg-2 at D28 versus 2-dose comparator vaccines at D28 will be higher than 80%.

Under the assumption that 15% of subjects will not be evaluable in the PPAS, 303 subjects in the VRVg-2 group and 101 subjects in each of the Verorab and Imovax Rabies vaccine groups must be enrolled in each age group of the study per the original plan, as Primary Series Cohort 1.

Updated Plan for Cohort 1 and Cohort 2 (Protocol Amendments 2, 3, and 4):

According to the latest results from the VAJ00001 study and to be conservative, the estimation of proportion of adult subjects with an RVNA titer ≥ 0.5 IU/mL at D28 was adjusted from 99% to 96.5% for both VRVg-2 and control vaccines. With the aim to secure the study power for the 2nd secondary immunogenicity NI objective at D28 and maintain the randomization ratio, 609 evaluable adults in the VRVg-2 group, and 203 evaluable adults in each of the control vaccine group (Verorab and Imovax Rabies) will be necessary to provide a power of 81.7% to demonstrate the 2nd secondary immunogenicity objective at D28, using the FM method.

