- Adult subjects: at D28, there will be about 570 and 190 evaluable subjects in VRVg-2 group and each of the comparator vaccine groups, respectively (pooled Cohort 1 and Cohort 2); at D42, there will be about 243 and 81 evaluable subjects in VRVg-2 group and each of the comparator vaccine groups, respectively (Cohort 1 only).

Moreover, 2 new secondary immunogenicity objectives were added, both with a NI margin of 10%:

- To demonstrate the NI of 2-dose VRVg-2 at D28 versus 3-dose Imovax Rabies at D42 in each age group
- To demonstrate the NI of 2-dose Imovax Rabies at D28 versus 3-dose Imovax Rabies at D42 in the overall subjects (pooled pediatric and adult subjects) in Cohort 1

Finally, the primary objective and all 5 key secondary immunogenicity objectives will be evaluated sequentially. Each of the key immunogenicity objective will be tested only if the previous objective is achieved.

Based on the updated study objectives and the adjusted number of evaluable subjects in the PPAS, the power to demonstrate each of the key immunogenicity objectives is presented [Table 12.1](#).

Table 12.1: Sample size and power estimation for primary and key secondary immunogenicity objectives.

Key Immunogenicity Objective	Age group	Evaluable N in the PPAS	Estimation/Margin	Power (%)
Primary Objective	Pediatric Subjects (Cohort[C] 1)	VRVg-2: 261 Verorab: 88	Seroconversion (SC) rate at D42: 99.0% NI margin: -5%	95.4 ^a
		VRVg-2: 261 Imovax Rabies: 88	Same as above	95.4 ^a
	Adult Subjects (C1)	VRVg-2: 243 Verorab: 81	Same as above	93.8 ^a
		VRVg-2: 243 Imovax Rabies: 81	Same as above	93.8 ^a
				Overall: 80.0^a
Key Secondary Objectives				
#1	Overall (Pooled Pediatric and Adult Subjects in C1)	VRVg-2: 504	Sufficiency threshold: SC rate at D42 \geq 99.0%, with lower limit (LL) of 95%CI \geq 97.0%	86.3^b
#2	Pediatric Subjects (C1)	VRVg-2: 261 Verorab: 88	SC rate at D28: 99.0% NI margin: -5%	95.4 ^a
		VRVg-2: 261 Imovax Rabies: 88	Same as above	95.4 ^a
	Adult Subjects (Pooled C1+C2)	VRVg-2: 570 Verorab: 190	SC rate at D28: 96.5% NI margin: -5%	93.8 ^a
		VRVg-2: 570 Imovax Rabies: 190	Same as above	93.8 ^a
				Overall: 80.1^a
#3	Pediatric Subjects (C1)	VRVg-2 at D28: 261 Imovax Rabies at D42: 88	SC rate at D28: 99.0% SC rate at D42: 99.0% NI margin: -10%	>99.9 ^a
	Adult Subjects (D28 from Pooled C1+C2, D42 from C1)	VRVg-2 at D28 (Pooled Cohort 1+ Cohort 2): 570 Imovax Rabies at D42: 81	SC rate at D28: 96.5% SC rate at D42: 99.0%NI margin: -10%	>99.9 ^a
				Overall: >99.9^a

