## 5.5 Determination of Sample Size and Power Calculation

### 5.5.1 Primary Series

#### Original Plan:

An alpha level of 2.5% (one-sided hypothesis) has been chosen to calculate the sample size.

Originally, assuming a proportion of subjects with an RVNA titer  $\geq 0.5$  IU/mL of 99% for both VRVg-2 and control vaccines in each age group at D42, a clinical acceptable difference of -5% for the difference of proportions at D42 between VRVg-2 and the control vaccines, and a power of at least 95% for each of the NI testing in the primary objective, with an unbalanced randomization ratio of 3:1:1 (VRVg-2: Verorab vaccine: Imovax Rabies vaccine), 258 evaluable subjects in the VRVg-2 group, and 86 evaluable subjects in each of the Verorab and Imovax Rabies vaccine groups who are planned to receive 3 vaccinations (at D0, D7 and D28) in primary series in each age group, will be necessary to provide a global power of 81.8% for the primary NI objective, using the Farrington and Manning (FM) method.

If the primary objective is met at D42, a total of 516 subjects evaluable in the VRVg-2 group will ensure 85.0% of power for the 1st secondary immunogenicity objective of superiority at D42. If the 1st secondary immunogenicity objective is met, overall power for the 2nd secondary immunogenicity NI objective of 2-dose VRVg-2 at D28 versus 2-dose comparator vaccines at D28 will be higher than 80%.

Under the assumption that 15% of subjects will not be evaluable in the PPAS, 303 subjects in the VRVg-2 group and 101 subjects in each of the Verorab and Imovax Rabies vaccine groups must be enrolled in each age group of the study per the original plan, as Primary Series Cohort 1.

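### The power tables leave out the fixed sequence, and for objectives 1 and 4 also the 99% criterion; objective 2 has about 56-58% power through the sequence, not 80.1%

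*SAP*

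**What the plan says.** SAP 5.5.1, under the Amendment 5 update, sets the testing rule: "Each of the key immunogenicity objective will be tested only if the previous objective is achieved". It then announces that "the power to demonstrate each of the key immunogenicity objectives is presented as below" and gives Table 5.7. Protocol 12.5.1 does the same ahead of Table 12.1 ("the power to demonstrate each of the key immunogenicity objectives is presented"), and the synopsis repeats the figures. Neither table is labelled conditional or stand-alone, and neither gives power through the sequence.

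SAP 5.1.2.2 defines success for objectives 1 (D42) and 4 (D28) by two conditions: an observed rate of 99.0% or more, and a Clopper-Pearson 95% lower limit of 97% or more. Rows 1 and 4 of Table 5.7 list both conditions but no assumed true rate. Row 4 also names D42, although objective 4 concerns D28.

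Protocol 12.5.1 gives the reason for the 690 adults of Cohort 2: "With the aim to secure the study power for the 2nd secondary immunogenicity NI objective at D28". The sizing sentence then quotes 81.7% power for that objective with no condition attached.

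**The concern.** In a fixed sequence, an objective is demonstrated only if it and every earlier objective pass. A figure built from one objective's own tests overstates the chance of making that claim, unless the earlier steps almost never fail. Objective 1 is not such a step. It stands ahead of the 2-dose non-inferiority claims, and six failures among 504 VRVg-2 subjects at D42 block those claims whatever Cohort 2 shows. If its power is itself overstated, the plan gives the wrong impression of what Cohort 2 secures. Objective 4 stands ahead of objective 5 in the same way.

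**Working it through.** **Inputs.** All are from SAP 5.5.1 and Table 5.7.
- Error rate: "An alpha level of 2.5% (one-sided hypothesis) has been chosen to calculate the sample size".
- Pediatric, D28 and D42: "about 261 and 88 evaluable subjects in VRVg-2 group and each of the comparator vaccine groups".
- Adults, D28: "at D28, there will be about 570 and 190 evaluable subjects in VRVg-2 group and each of the comparator vaccine groups".
- Adults, D42: "at D42, there will be about 243 and 81 evaluable subjects in VRVg-2 group and each of the comparator vaccine groups".
- True rates: 99.0% at D42 in both age groups, 99.0% at D28 in pediatric subjects, 96.5% at D28 in adults.
- Margins: -5% for the primary objective and objective 2; -10% for objective 3.

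**1. Reproducing the non-inferiority figures.** Farrington-Manning power is Φ[(0.05 − 1.96·SE0)/SE1], where SE0 uses the rates constrained to the margin and SE1 the assumed rates.
- 261 v 88 at 99%: (0.05 − 1.96×0.01496)/0.01227 = 1.69, giving 95.4%.
- 243 v 81 at 99%: (0.05 − 1.96×0.01551)/0.01277 = 1.54, giving 93.8%.
- 570 v 190 at 96.5%: (0.05 − 1.96×0.01342)/0.01540 = 1.54, giving 93.8%.

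Primary: 0.9541² × 0.9377² = 80.0%. Objective 2: 0.9541² × 0.9382² = 80.1%. Both match the table, so 80.1% contains objective 2's own four comparisons and no earlier step.

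**2. Reproducing rows 1 and 4 (exact binomial, true rate 99%).**

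| | Most failures allowed | Observed rate at that count | Exact lower limit | Power |
|---|---|---|---|---|
| Obj. 1, lower limit only | 7 of 504 | 98.61% | 97.16% | 86.3% (as stated) |
| Obj. 1, both criteria | 5 of 504 | 99.01% | 97.70% | 60.9% |
| Obj. 4, lower limit only | 15 of 831 | 98.19% | 97.04% | 98.9% (as stated) |
| Obj. 4, both criteria | 8 of 831 | 99.04% | 98.11% | 54.9% |

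The stated figures appear only when the 99% criterion is left out.

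**3. Row 4 at row 2's rates.** Expected failures are 261×0.01 + 570×0.035 = 22.6 of 831, a blended rate of 97.3%. The exact chance of at most 8 failures is about 0.03%. Even at most 15 (lower limit only) has a chance of only 5.9%. Row 4 therefore assumes 99% in adults at D28, where rows 2 and 3 assume 96.5%.

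**4. Power through the sequence (%).** The product column multiplies the stated figures, taking >99.9 as 0.999. The simulated columns apply the planned rules (Newcombe-Wilson limits, VRVg-2 arm shared between comparisons) in one million trials per dependence assumption. D28 and D42 failures range from independent to fully nested.

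| Through | Stated, own tests | Product of stated | Simulated, full rules | Simulated, lower limit only in obj. 1 and 4 |
|---|---|---|---|---|
| Primary | 80.0 | 80.0 | 96.2-96.3 | 96.2-96.3 |
| Obj. 1 | 86.3 | 69.0 | 60.9 | 85.8 |
| Obj. 2 | 80.1 | 55.3 | 56.5-58.1 | 79.5-81.2 |
| Obj. 3 | >99.9 | 55.2 | 56.5-58.1 | 79.5-81.2 |
| Obj. 4 | 98.9 | 54.6 | under 0.1 | 5-6 |
| Obj. 5 | 90.0 | 49.2 | at most obj. 4 | at most obj. 4 |

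Objective 5 was not simulated; it cannot exceed objective 4's cumulative figure. If the adult D28 rate were 99%, objective 4 would reach 33-40% cumulatively for a D28-D42 correlation of 0 to 0.5.

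**5. Where the loss arises.** Simulated non-inferiority power is higher than the Farrington-Manning product: 96% against 80.0% for the primary, and 93% against 80.1% for objective 2 alone. With every step of the sequence kept but only the lower limit required at objective 1, objective 2 stays near 80%. The fall to 56-58% comes from the 99% criterion. The 55.3% product lands nearby because two errors offset: non-inferiority power too low, objective 1 power too high.

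**The case against.** The strongest reply has four parts.

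First, parts of the text are conditional. The original plan words objective 1's power as given success on the primary, and the update words the D28 superiority power as given success on objective 2. The testing rule also stands directly above Table 5.7, and per-objective power beside a stated sequence is common. This stands for those sentences. It does not cover the tables or the sentence sizing Cohort 2, and it does not rescue 86.3% or 98.9%, which are not the power of the stated rules even in isolation.

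Second, a reader might infer that ignoring the sequence is by itself what turns 80.1% into 57%. The documents do not support that: with objective 1 judged on its lower limit only, simulated cumulative power is 79.5-81.2%, in line with the stated figure.

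Third, a reader might infer that the order of objectives is wrong and must change. The order is prespecified and protects the type I error, and part of the rationale for the objectives is redacted. Where the 99% tests belong is a design judgement.

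Fourth, enrolment is complete (1708 subjects), and a power table alters no estimate, interval, decision rule or error rate. That is correct. It limits the point to what the plan claims it can show.

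**Conclusion.** The point holds in this form. The tables present power to demonstrate each key objective without the sequence, and rows 1 and 4 omit half of their success rule. Correct stand-alone figures at a true 99% are 60.9% and 54.9%. Objective 2 has about 56-58% power through the sequence, mainly because of the 99% criterion at objective 1. At the table's own D28 rates, objectives 4 and 5 are close to unreachable.

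The stand-alone figures are exact. The 56-58% rests on the assumed rates, the projected evaluable numbers and the D28-D42 dependence. Using only the stated powers and no dependence assumption, the cumulative figure for objective 2 lies between 0.800 + 0.863 + 0.801 − 2 = 46.4% and 80.0%; a normal model linking the objectives, with 86.3% kept for objective 1, gives 59-62%. If true rates exceed 99% at D42 or 96.5% in adults at D28, the power is higher. The validity of the tests is not in question.

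**What to change.** In SAP Table 5.7, protocol Table 12.1 and the synopsis table:
1. Recompute rows 1 and 4 with both criteria. State the assumed true rates, use D28 rates in row 4 that agree with row 2, and correct row 4's D42 label. Labelling the present 86.3% and 98.9% as stand-alone power would certify two wrong figures.
2. Label the per-objective figures as stand-alone.
3. Add a column of cumulative power, obtained by simulating the actual decision rules, with the D28-D42 dependence assumption stated and objective 5 included.
4. Replace the unconditional statement of about 80% power for objective 2 with the cumulative figure, or make it explicitly conditional on the primary objective and objective 1.

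The cost is a short simulation, one column and a few sentences. The stated figures become less favourable.

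Moving the two 99% tests behind the non-inferiority tests before unblinding is optional and not part of this fix. In the order primary, 2, 3, 1, 4, objectives 2 and 3 would rise to about 89-90% and objective 1 would fall to about 57%. Placing objective 5 ahead of objective 1 as well was not evaluated.

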**Table 5.7: Sample size and power estimation for primary and key secondary immunogenicity objectives**

Key Immunogenicity Objective	Age group	Evaluable N in the PPAS	Estimation/Margin	Power (%)
Primary Objective	Pediatric Subjects (Cohort[C] 1)	VRVg-2: 261 Verorab: 88	Seroconversion (SC) rate at D42: 99.0% NI margin: -5%	95.4 a
		VRVg-2: 261 Imovax Rabies: 88	Same as above	95.4 a
	Adult Subjects (C1)	VRVg-2: 243 Verorab: 81	Same as above	93.8 a
		VRVg-2: 243 Imovax Rabies: 81	Same as above	93.8 a

				Overall: 80.0a
Key Secondary Objectives				
#1	Overall (Pooled Pediatric and Adult Subjects in C1)	VRVg-2: 504	Sufficiency threshold: SC rate at D42 $\geq$ 99.0%, with lower limit (LL) of 95%CI $\geq$ 97.0%	86.3b
#2	Pediatric Subjects (C1)	VRVg-2: 261 Verorab: 88	SC rate at D28: 99.0% NI margin: -5%	95.4 a
		VRVg-2: 261 Imovax Rabies: 88	Same as above	95.4 a
	Adult Subjects (Pooled C1+C2)	VRVg-2: 570 Verorab: 190	SC rate at D28: 96.5% NI margin: -5%	93.8 a
		VRVg-2: 570 Imovax Rabies: 190	Same as above	93.8 a
Overall: 80.1a				
#3	Pediatric Subjects (C1)	VRVg-2 at D28: 261 Imovax Rabies at D42: 88	SC rate at D28: 99.0% SC rate at D42: 99.0% NI margin: -10%	>99.9 a
	Adult Subjects (D28 from Pooled C1+C2, D42 from C1)	VRVg-2 at D28 (Pooled Cohort 1+ Cohort 2): 570 Imovax Rabies at D42: 81	SC rate at D28: 96.5% SC rate at D42: 99.0%NI margin: -10%	>99.9 a
	Overall: >99.9a			
#4	Overall (Pooled Pediatric and Adult Subjects in Pooled C1 and C2)	VRVg-2: 831	Sufficiency threshold: SC rate at D42 $\geq$ 99.0%, with LL of 95%CI $\geq$ 97.0%	98.9b
#5	Overall (Pooled Pediatric and Adult Subjects in C1 only)	Imovax Rabies at D28: 168 Imovax Rabies at D42: 168	SC rate at D28: 96.5% SC rate at D42: 99.0% NI margin: -10%	90.0c

a Power calculated using Farrington and Manning (FM) method.

b Power calculated using Binomial Exact method.

c Power calculated using simulation (10000 times, assuming correction coefficient [Rho]=0.5), based on general linear model (GLM) for repeated measured data with categorical response under binomial distribution (link function=identify).

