### 5.1.2.2 Statistical Methods

The hypotheses associated with the secondary immunogenicity objectives will be tested only if the primary objective is demonstrated, and then each of the secondary immunogenicity objectives will be evaluated sequentially following a fixed-sequence method as specified below (5) (6) (7).

This method allows to conclude on any of the hypothesis testing conducted at one-sided 0.025 nominal alpha without inflation of overall Type I error, provided the sequence specified hereafter is respected:

- **Secondary immunogenicity objective 1: Superiority in the 3-dose VRVg-2 group at D42**

Only if the primary objective is achieved at D42, the superiority of VRVg-2 group at D42 will be assessed on overall subjects in VRVg-2 group.

The null hypothesis will be rejected and the 1st secondary immunogenicity objective will be achieved if the observed proportion of subjects with an RVNA titer  $\geq 0.5$  IU/mL at D42 in VRVg-2 group is at least 99.0%, and the lower limit of the 95% CI of the proportion calculated using the exact binomial distribution (Clopper Pearson method) (1) is at least 97%.

- **Secondary immunogenicity objective 2: NI testing of 2-dose VRVg-2 at D28 versus 2-dose Verorab and Imovax Rabies at D28**

Only if the 1st secondary immunogenicity objective is achieved, based on the same statistical approach for the primary objective, the non-inferiority of VRVg-2 compared to each of the comparator vaccines will be tested at D28, in each age group (ie, in pediatric subjects and adult subjects, respectively), with the two-sided 95% CI of the difference of the 2 proportions at D28, calculated using Wilson score method without continuity correction (2).

The null hypothesis will be rejected if the lower limit of the two-sided 95% CI of the difference of the 2 proportions ( $P_{VRVg-2} - P_{control}$ ) is  $> -5\%$ .

The 2nd secondary immunogenicity objective of NI at D28 will be demonstrated if all null hypotheses are rejected.

- **Secondary immunogenicity objective 3: NI testing of 2-dose VRVg-2 at D28 versus 3-dose Imovax Rabies at D42**

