Only if the 2nd secondary immunogenicity objective is achieved, based on the similar statistical approach for the primary objective, the non-inferiority of 2-dose VRVg-2 compared to 3-dose Imovax Rabies will be tested, in each age group (ie, in pediatric subjects and adult subjects, respectively), with the two-sided 95% CI of the difference of the 2 proportions, calculated using Wilson score method without continuity correction (2).

The null hypothesis will be rejected if the lower limit of the two-sided 95% CI of the difference of the 2 proportions ( $P_{VRVg-2 \text{ at D28}} - P_{\text{Imovax Rabies at D42}}$ ) is  $> -10\%$ .

The 3rd secondary immunogenicity objective will be demonstrated if all null hypotheses are rejected.

In addition, supplemental analysis will be performed based on NI margin of -5%, using the same statistical method.

- **Secondary immunogenicity objective 4: Superiority in the 2-dose VRVg-2 group at D28**

Only if the 3rd secondary immunogenicity objective is achieved, based on the same statistical approach for the 1st secondary immunogenicity objective, the superiority of VRVg-2 group at D28 will be assessed on overall subjects in VRVg-2 group.

The null hypothesis will be rejected and the 4th secondary immunogenicity objective will be achieved if the observed proportion of subjects with an RVNA titer  $\geq 0.5$  IU/mL at D28 in VRVg-2 group is at least 99%, and the lower limit of the 95% CI of the proportion calculated using the exact binomial distribution (Clopper Pearson method) (1) is at least 97%.

- **Secondary immunogenicity objective 5: NI testing of 2-dose Imovax Rabies at D28 versus 3-dose Imovax Rabies at D42**

Only if the 4th secondary objective is achieved, the 5th secondary immunogenicity objective will be assessed on overall subjects in Imovax Rabies group in Cohort 1 only, using the statistical methods mentioned below, based on NI margin of -10%.

In addition, supplemental analysis will be performed based on NI margin of -5%, using the same statistical method.

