**Updated Plan for Cohort 1 and Cohort 2 (Protocol Amendments 2, 3 and 4):**

Then, according to the latest results from the VAJ00001 study and to be conservative, the estimation of proportion of adult subjects with an RVNA titer  $\geq 0.5$  IU/mL at D28 was adjusted from 99% to 96.5% for both VRVg-2 and control vaccines. With the aim to secure the study power for the 2nd secondary immunogenicity NI objective at D28 and maintain the randomization ratio, 609 evaluable adults in the VRVg-2 group, and 203 evaluable adults in each of the control vaccine group (Verorab and Imovax Rabies) will be necessary to provide a power of 81.7% to demonstrate the 2nd secondary immunogenicity objective at D28, using the FM method.

If the 2nd secondary immunogenicity objective is met at D28, a total of 867 subjects evaluable in the VRVg-2 group will ensure 99.2% of power for the secondary objective of superiority for VRVg-2 at D28 in the overall subjects (pooled pediatric and adult subjects).

Therefore, under the attrition rate of 15%, 690 additional adults (414 in VRVg-2; 138 in Verorab; 138 in Imovax Rabies) were planned to be enrolled in the study as Cohort 2 to receive 2 vaccinations at D0 and D7 in the primary series. Those 690 additional adults in Cohort 2 were planned to be pooled with the 505 adults enrolled in Cohort 1, for testing the 2nd secondary NI objective at D28. The 414 additional adults in VRVg-2 group in Cohort 2 were planned to be pooled with the 303 pediatric subjects and 303 adult subjects in VRVg-2 group in Cohort 1, for testing the secondary superiority objective for VRVg-2 at D28.

Therefore, a total of 1700 subjects (505 pediatric subjects and 1195 adult subjects) were planned to be enrolled in total by 2 Cohorts, including 505 pediatric subjects and 505 adult subjects in Cohort 1 who are planned to receive 3 doses of vaccinations in the primary series, and 690 adult subjects in Cohort 2 who were planned to receive 2 doses of vaccinations in the primary series.

As a consequence, a total of 1708 subjects (505 pediatric subjects and 1203 adult subjects) were actually enrolled, including 505 pediatric subjects and 505 adult subjects in Primary Series Cohort 1 and 698 adult subjects (including 8 replacements) in Primary Series Cohort 2.

The 3:1:1 design is chosen to optimize the NI testing for immunogenicity and to increase the size of the safety database.

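### The stated power for key secondary objectives 4 (98.9%) and 1 (86.3%) omits the observed-99% condition; at a true 99% rate the full rule has 54.9% and 60.9%

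*SAP*

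**What the plan says.** SAP section 5.1.2.2 sets a two-part success rule. For objective 1 the null is rejected only if the observed response "at D42 in VRVg-2 group is at least 99.0%, and the lower limit of the 95% CI of the proportion", calculated by Clopper-Pearson, is at least 97%. Objective 4 has the same rule at D28: the observed response "at D28 in VRVg-2 group is at least 99%, and the lower limit of the 95% CI of the proportion" must again be at least 97%. Protocol sections 12.1.2.1 and 12.1.2.2 agree.

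SAP Table 5.7 gives these powers:

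- Row #1, "Overall (Pooled Pediatric and Adult Subjects in C1": N=504, power 86.3%.
- Row #4, "Overall (Pooled Pediatric and Adult Subjects in Pooled C1 and C2": N=831, power 98.9%.

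The footnote to both rows reads "Power calculated using Binomial Exact method". In each row the assumption cell holds the success threshold and no assumed true rate. Row #4 dates that threshold D42, although objective 4 is assessed at D28.

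SAP section 5.5.1 also gives figures from earlier stages of the design: "a total of 516 subjects evaluable in the VRVg-2 group will ensure 85.0% of power for the" first secondary objective, and "a total of 867 subjects evaluable in the VRVg-2 group will ensure 99.2% of power for the secondary objective of superiority" at D28. The same section assumes 99% at D42. For adults at D28 it lowers the assumption from 99% to 96.5%, "according to the latest results from the VAJ00001 study and to be conservative"; rows #2 and #3 use 96.5%.

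Protocol section 12.5.1, Protocol Table 12.1 and the synopsis power table carry the same powers.

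**The concern.** A power figure for a two-part rule should be the probability that both parts are met. Here the observed-99% requirement is stricter than the lower-limit requirement at every sample size the plan uses, so a calculation on the lower limit alone counts as successes some results that the SAP would declare failures. For example, 15 failures in 831 is an observed rate of 98.19%, and 7 in 504 is 98.61%.

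Row #4 raises a second question. A single pooled D28 rate of 99% is not what the plan assumes elsewhere for the adults, who make up 570 of the 831.

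Both objectives are gates in the fixed sequence. Objective 1 must succeed before objectives 2 to 5 can be tested, and objective 4 before objective 5. If their powers are overstated, so is the chance that the later confirmatory claims are ever tested.

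**Working it through.** **Inputs.** N=504 (261 children + 243 adults) and N=831 (261 + 570), from Table 5.7. N=516 and N=867, from SAP 5.5.1. Decision rule from SAP 5.1.2.2. True rate 99%: stated for D42 in SAP 5.5.1, and inferred for row #4 because it reproduces the stated figure.

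**Formulas.** With x responders out of n, the Clopper-Pearson lower limit is the 0.025 quantile of Beta(x, n − x + 1). Let X be the number of failures, X ~ Bin(n, 1 − p). If c is the largest number of failures that still meets a condition, power is P(X ≤ c).

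**Failures allowed.**

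- Lower limit ≥ 97%: 7 of 504 (limit 97.16%; 8 gives 96.90%), 7 of 516, 15 of 831 (97.04%; 16 gives 96.89%) and 16 of 867.
- Observed rate ≥ 99%: 5 of 504 (499/504 = 99.01%), 5 of 516, 8 of 831 (823/831 = 99.04%) and 8 of 867. One more failure gives 498/504 = 98.81% or 822/831 = 98.92%, so rounding to one decimal does not rescue it.

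**Power at a true 99%.**

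| Objective | N | Stated | Lower limit only | Both conditions |
|---|---|---|---|---|
| 1 (current) | 504 | 86.3% | P(X ≤ 7) = 86.3% | P(X ≤ 5) = 60.9% |
| 1 (original plan) | 516 | 85.0% | P(X ≤ 7) = 85.0% | P(X ≤ 5) = 58.8% |
| 4 (current) | 831 | 98.9% | P(X ≤ 15) = 98.9% | P(X ≤ 8) = 54.9% |
| 4 (amendments 2–4) | 867 | 99.2% | P(X ≤ 16) = 99.2% | P(X ≤ 8) = 49.9% |

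All four stated figures match the lower-limit calculation. None matches the full rule.

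**Objective 4 with separate age-group rates.** Here X = Bin(261, 1 − p_child) + Bin(570, 1 − p_adult), and power is P(X ≤ 8).

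| Adults | Children 99% | Children 100% |
|---|---|---|
| 99.0% | 54.9% | 87.8% |
| 98.5% | 21.6% | 51.6% |
| 98.0% | 6.0% | 19.6% |
| 96.5% | 0.03% | 0.19% |

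At the rates in row #2 (children 99%, adults 96.5%) the expected number of failures is 261 × 0.01 + 570 × 0.035 = 22.6, against 8 allowed. Even the lower-limit condition alone then has only 5.9% power. At 99.5% throughout, the full rule has 97.4%.

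**Rates the full rule needs.** Objective 4 at N=831 needs a true pooled rate of 99.23% for 80% power and 99.35% for 90%. Objective 1 at N=504 needs 99.22% for 80%. To deliver the stated powers, the true rates would have to be about 99.57% (objective 4) and 99.31% (objective 1).

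**The case against.** The arithmetic is not in dispute; the objections concern its reach.

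- **Row #4's rate is inferred.** The documents never state it, and the full rule would give 98.9% at about 99.57%. That value appears nowhere in the plan, however, while 99% with the lower limit alone reproduces all four figures. The inference is strong, but it remains an inference.
- **The table is per objective.** It does not claim 86.3% as the chance of reaching objective 2. It already shows 80.0% for the primary objective, and simple multiplication gives 0.800 × 0.863 = 69.0%. This stands: the fair comparison with the 60.9% ceiling is about 69%, and the gap is smaller than 86.3% against 60.9% suggests. The corrected figures are themselves per objective.
- **96.5% was chosen as conservative.** Protocol 5.4.1 reports 100% in children in the study behind it, and adult rates taken 14 days after dose 2, where this trial samples at 21 days. This also stands: 0.03% marks the low end and is not a forecast, and the intermediate scenarios are illustrations. It does not support 98.9% at a uniform 99%.
- **The 85.0% and 99.2% sentences are design history and conditional on the preceding objective.** A simulation at 99% throughout, conditioning on the preceding non-inferiority test, gives about 60.1% and 50.5% in place of 58.8% and 49.9%. An annotation is enough, and the difference is immaterial.
- **Enrolment is complete, and the gating is already stated.** Both are true. The correction concerns what the plan reports, and only the numerical consequence of the gating would be new.

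**Conclusion.** The point holds. The stated powers for objectives 1 and 4 describe the lower-limit condition alone. For the rule the SAP will apply, power at a true 99% is 60.9% rather than 86.3% for objective 1 (N=504), and 54.9% rather than 98.9% for objective 4 (N=831). The objective 1 figure rests on the plan's own 99% at D42. The objective 4 figure rests on the 99% inferred for D28; with children at 99%, it falls to 0.03% at the plan's conservative adult rate.

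At 99%, the chance of reaching any of objectives 2 to 5 is at most 60.9%. The chance of testing objective 5 is also at most the objective 4 figure. Row #4 additionally lacks an assumed D28 rate, is inconsistent with rows #2 and #3 for the same adults, and carries the wrong day. This should be fixed as a reporting correction: decision rules, testing order, type I error control and data are unaffected.

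**What to change.** In SAP Table 5.7, Protocol Table 12.1 and the synopsis power table:

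1. State the assumed D42 rate for row #1 and the assumed D28 rate or rates for row #4. The synopsis table has no assumption column, so a footnote will do there.
2. In row #4 of Tables 5.7 and 12.1, change the day from D42 to D28.
3. Give the power of the full two-part rule: 60.9% for objective 1 (N=504) and 54.9% for objective 4 (N=831), both at 99%. For objective 4, explain the departure from 96.5% in adults. A short range is advisable: 0.03% at 99%/96.5% (children/adults), 6.0% at 99%/98.0%, 21.6% at 99%/98.5%, and 97.4% at 99.5% throughout.
4. Annotate the 85.0% (N=516) and 99.2% (N=867) sentences as lower-limit-only figures; the full rule gives 58.8% and 49.9% at 99%.
5. Add one sentence after the existing gating statement: the chance of testing objectives 2 to 5 is capped by objective 1, and that of objective 5 also by objective 4.

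The cost is a text and table revision in two documents, with two stated powers becoming less favourable. No sample size, data, decision rule or testing order changes.
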